Whether intervening on the complement system would slow the progression of mechanically/surgically induced osteoarthritis is not yet known in humans. In humans with advanced osteoarthritis undergoing total knee arthroplasty, elevated activity of the complement system has been established. Although the [name] lab has demonstrated increase activation of the complement system in early OA (Fig. below; Wang et al., 2011), whether meniscal tears are associated with activation of the complement system and alteration of gene expression in the synovial lining has not been previously investigated. Establishing whether this is the case with joint fluid aspiration and a synovial biopsy of patients undergoing arthroscopic meniscectomy for a degenerative meniscus tear, since they are believed to be patients with early osteoarthritis, will be a major step in further understanding the role of complement in the progression of osteoarthritis and potentially developing pharmacologic intervention strategies to slow osteoarthritis progression. This the focus of an exploratory aim of the proposed work.

Preliminary Studies and Current Status of the Field

Prospective Study on Arthroscopic Meniscectomy outcomes at the VA Palo Alto

We have performed a preliminary study on patients at the Palo Alto VA hospital undergoing arthroscopic meniscectomy (Mirza et al., 2011). In this study, we prospectively followed patients presenting to the orthopedic clinic with meniscus tears and who underwent arthroscopic meniscectomy. 78 subjects with a mean age of 51 years scheduled for knee arthroscopy for meniscal tears were enrolled. 45 subjects were available for final review at one year. History of acute injury within 6 months of surgery, Kellgren-Lawrence arthritis grade, and MRI appearance of meniscus tear (degenerative or not) was recorded for each patient. Pre- and one year postoperative WOMAC and WOMET were used to evaluate surgical outcome with statistical analysis done by ANOVA.

The Western Ontario and McMaster Universities Osteoarthritis Index (WOMAC) (Bellamy et al., 1988) and the more recent Western Ontario Meniscal Evaluation Tool (WOMET) (Kirkley et al., 2007) are self-administered validated outcome tools for osteoarthritis of the knee and meniscal tears of the knee.

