Proteomic survey of OA synovial fluid. The [name] lab subjected OA synovial fluid samples to 2-dimensional gel electrophoresis followed by mass spectrometric analysis (the [name] Laboratory runs a mass spectrometry core for the VA Palo Alto). 183 distinct proteins were identified, and the DAVID bioinformatic algorithm (<http://david.abcc.ncifcrf.gov/>) was used to determine the pathways represented by the identified proteins along with the Bonferroni-corrected *P* value for each pathway (Fig. 8 below).

Complement components are aberrantly expressed and activated in OA joints.

Complement proteins identified in our proteomic survey of OA synovial fluid are listed in Figure 9 below. Components of the classical (C1s & C4a) and alternative (factor B) pathways, the C3 and C5 convertases, and the C5, C7, and C9 components of MAC were aberrantly expressed in OA (Wang et al, 2011).

[figure not shown]
[figure not shown]
[figure not shown]

Fig. 9. Complement components are aberrantly expressed and activated in OA joints. Complement proteins identified by 2-dimensional gel electrophoresis and mass spectrometric analysis as expressed in OA ($n = 10$) compared to healthy ($n = 10$) synovial fluids. In the schematic of the complement cascade, blue-filled circles denote the complement effectors and inhibitors identified as expressed in OA.

[figure not shown]
Increased complement proteins in OA synovial fluid. We used ELISA to verify the presence of complement in synovial fluid in OA, and found that C3a and MAC (C5b-9) levels are increased in OA compared to healthy synovial fluid, early in the course of OA (Fig. 10 below; Wang et al, 2011). Elevated levels of MAC in OA synovial fluids have been reported previously.

[figure not shown]
MAC deposition in OA cartilage and synovium. We performed immunohistochemistry on cartilage and synovium from patients with end-stage OA by using an antibody specific for MAC (C5b-9). Staining with anti-C5b-9 demonstrates the presence of MAC on and around chondrocytes in the OA cartilage, and on and around synoviocytes in the OA synovium (Fig. 11 below). Our results are consistent with previous reports demonstrating C3 on articular surfaces and MAC on and around chondrocytes¹⁹ in OA cartilage (Wang et al, 2011).

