Imaging of muscle cross sectional area: Muscle cross sectional area measurement can provide additional information regarding the functional consequences of meniscectomy. We will image the thigh of patients at enrollment, and at two-year follow up to determine if patients undergoing meniscectomy vs. lavage have greater changes in muscle cross sectional area. Images will be obtained using a rapid axial thigh scan with IDEAL fat/water separation using a 3D spoiled gradient echo sequence. The data will have 1 mm in-plane resolution and 5 mm slice thickness. Acquisition time will be approximately 2 minutes. Muscle cross sectional area will then be determined as previously described {Walton 1997}.

Research Design and Methods

In this study we propose a prospective, randomized, blinded, and controlled clinical trial of arthroscopic meniscectomy in patients between the ages of 45 and 70 with degenerative meniscus tears.

Patient Selection:

Subjects will be recruited from the orthopedic clinic at the VA Palo Alto Healthcare System. Eligible subjects will meet the following inclusion criteria:

1. Age between 45 and 70 years
2. Degenerative meniscus tear as seen by a standard clinical MRI scan
3. A complaint of “mechanical symptoms” which would include popping, catching, or locking of the knee
4. Persistent symptoms for a minimum of three months despite conservative management including anti-inflammatory medications and physical therapy
5. Patient is enrolled for arthroscopic meniscectomy
6. The subject agrees to study follow-up schedule and signs informed consent.

The following exclusion criteria will be enforced:

1. Radiographic osteoarthritis of the knee in any compartment that is greater than KL grade 2
2. Prior knee arthroscopy within two years of study enrollment
3. Unable to have an MRI scan
4. Does not agree to participate

General Study Plan:

Patients who satisfy the inclusion and exclusion criteria and are scheduled for arthroscopic meniscectomy will be approached during their preoperative visit to participate in the study. They will be enrolled when they give informed consent.

Preoperative study related evaluation:

Prior to undergoing surgery, the patient will have the following evaluations:

1. The patient will fill out the WOMET (Kirkley et al., 2007) and WOMAC (Bellamy et al., 1988) surveys.
2. The patient will undergo a gait analysis
3. The patient will have MRI of the knee and thigh.

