4. The patient will have standing radiographs of the affected knee.

Evaluation at the time of surgery:

At the time of surgery, the patient will be randomized to treatment with either an arthroscopic partial meniscectomy or arthroscopic lavage. Randomization will be done by opening a sealed envelope in the operating room prior to the procedure. To ensure balanced numbers in the two surgical conditions, especially at the time of the interim look, randomization will be done by permuted blocks of size 10, thereby ensuring 5 patients in each group at every increment of 10 enrollees.

Upon initiation of the surgery, a sample of synovial tissue and synovial fluid will be obtained for biochemical analysis. During the operation, the status of the knee joint will be documented. This will include classifying the degree of chondromalacia according to the Outerbridge classification in all three compartments of the knee, and documenting the geometry and pattern of meniscus tear type. Video and photographs will be taken to assist with this documentation and will be stored in a secure manner.

During the operation, the meniscus will be carefully probed. If a large unstable flap of tissue can be displaced into the articulation (such as a bucket handle tear) this torn fragment will be debrided regardless of the result of randomization. This will be done as it is widely believed that it is inappropriate to leave such an unstable tear untreated. Any other tear types that do not result in an unstable flap that can be displaced into the articulation will be either retained or debrided, depending on the result of randomization.

All postoperative contact from this point forward will be made by study personnel who were not involved in the surgery and who do not have knowledge of the randomization result.

At 2 weeks and 6 weeks:

The patient will have regularly scheduled clinic visits at 2 and 6 weeks that are not a part of the study but are just a part of the routine postoperative care of knee arthroscopy patients. Postoperative care as deemed necessary by the treating physician will be provided and could include pain and/or anti-inflammatory medications. Physical therapy is rarely needed. All provided treatments will be recorded in the chart.

Evaluation at 3 months:

1. The patient will fill out WOMET and WOMAC surveys.
2. The patient will undergo gait analysis.
3. The patient will have an MRI of the knee

Evaluation at 6 months:

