We will test the hypothesis that increased complement activation, levels of inflammatory cytokines and/or levels of cartilage metabolism biomarkers are associated with accelerated cartilage loss. Biomarkers of cartilage metabolism (Table 3 below) as well as inflammatory cytokines (Table 4 below) will be measured as indicated. The rationale for characterizing inflammatory cytokines, including IL-1 α , IL-6 and TNF, is based on the putative role of these cytokines in driving low-grade inflammation that might contribute to the pathogenesis of OA. Studies on human samples and in mouse models have suggested a role for IL-1 α and other cytokines in OA pathogenesis. Further, IL-1 α and other cytokines modulate neural signals arising from painful stimuli and may thereby exacerbate gait dysfunction in OA. The rationale for analyzing complement components is based on data from our laboratory (Wang et al, 2011) demonstrating elevations of complement components in OA synovial fluid and tissue, and on our data demonstrating that C5-deficient mice are protected against OA (Wang et al, 2011). The cartilage degradation product COMP have been shown by [name]

laboratory to be elevated following exercise, and certain markers of cartilage degradation or synthesis are thought to reflect cartilage turnover, disease severity, or disease progression in OA. The metalloproteinases (MMP) 3 and 13 mediate the proteolytic digestion and subsequent breakdown of cartilage in OA. For certain markers, such as certain collagen degradation products, there are findings suggesting that urine provides a more reliable sample source as compared to serum. We will use the sample source previously demonstrated to be most robust for detection of the biomarker. We will use commercially available ELISA/EIAs (Tables below) to measure the levels of select complement components, cytokines, and cartilage metabolism biomarkers in serum and synovial fluid samples.

Description	Biological fluid to be tested	Symbol	Units	Average (Standard deviation)	Kit source
Cartilage oligomeric matrix protein	serum	COMP	U/L	12.62(4.2)	Pacific Biomarkers
Hyaluronic acid	serum	HA	ng/ml	11.4(4.5)	Corgenix
Chondroitin sulfate 846	serum	CS-846	ng/ml		Ibex
Matrix metalloproteinase-3	serum, SF	MMP-3	ng/ml	64(199)	RnD Systems
Matrix metalloproteinase-13	serum, SF	MMP-13	ng/ml	54(18)	RnD
Type II collagen neopeptide	Serum	C2C	ng/ml		Systems
Keratan sulfate	serum	KS-5D4	ng/ml	27(19)	Ibex

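### The exploratory aim on meniscal tears and complement or synovial gene expression cannot be estimated from the planned samples and analyses, and the biomarker methods test a different hypothesis

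*Combined protocol and SAP*

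**What the plan says.** Under Understanding mechanisms of osteoarthritis progression, the Background describes as uninvestigated "whether meniscal tears are associated with activation of the complement system and alteration of gene expression in the synovial lining". It proposes to find out by "joint fluid aspiration and a synovial biopsy of patients undergoing arthroscopic meniscectomy for a degenerative meniscus tear", and adds: "This the focus of an exploratory aim of the proposed work".

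Four other places bear on this:

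- **Patient Selection.** Inclusion criterion 2 is "Degenerative meniscus tear as seen by a standard clinical MRI scan".
- **Evaluation at the time of surgery.** "Upon initiation of the surgery, a sample of synovial tissue and synovial fluid will be obtained for biochemical analysis". This applies to both arms. Outerbridge grade is recorded in all three compartments at the same operation.
- **Biomarker analysis of synovial and serum samples.** The hypothesis stated here is that "increased complement activation, levels of inflammatory cytokines and/or levels of cartilage metabolism biomarkers are associated with accelerated cartilage loss". The assays described are commercial immunoassays and a 50-cytokine bead array on serum and synovial fluid.
- **Power calculations & bioinformatic analysis.** The cartilage-loss hypothesis is repeated. A two-sample test is sized at 29 per group for an 8-marker index and 43 per group for a 6-marker index. The two groups are not identified.

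**The concern.** An association with tear status needs tear status to vary among the knees compared, or a named outside group without tears. The trial sections provide neither. Complement levels would be described in patients who all have tears, and the plan states nothing against which to judge activation. The methods then test another hypothesis, so the aim and the analysis do not meet.

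Patients give a synovial biopsy and joint fluid partly for this purpose, and the Background presents the answer as an important step towards drug strategies. A report that followed the Background wording could draw a conclusion about tears that the planned data cannot support.

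**Working it through.** **1. Does tear status vary among trial samples?** No. The inclusion criterion requires a tear in every patient.

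**2. Do the randomised arms supply a contrast?** No. Tissue and fluid are collected as surgery starts, before the meniscus is resected or left. A difference between arms in these samples would be chance.

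**3. Is a tear-free sample named?** Not for the trial. Patient Selection, the visit schedule and the biomarker sections mention no healthy donor, contralateral-knee or other tear-free specimen. Healthy material appears only in preliminary work: a proteomic survey "as expressed in OA ($n = 10$) compared to healthy ($n = 10$) synovial fluids" (Fig. 9 legend), an ELISA comparison of C3a and MAC with healthy fluid, and public healthy expression profiles (Fig. 14 legend). Nothing says these will be compared with trial samples.

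**4. Can the gene-expression half be addressed?** Synovial tissue is collected, but every assay described measures protein in serum or synovial fluid. No expression assay on trial synovium appears.

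**5. What does the plan's own sample size refer to?** Inputs from Power calculations & bioinformatic analysis: difference 0.25, variance 1/8 or 1/6 (independent markers), two-sided alpha 0.05, power 0.80.

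n per group = 2 × variance × (1.960 + 0.842)² / 0.25²

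| Index | Normal formula | t-test | Plan |
|---|---|---|---|
| 6 markers | 2 × (1/6) × 7.849 / 0.0625 = 41.9, so 42 | 43 | 43 |
| 8 markers | 2 × (1/8) × 7.849 / 0.0625 = 31.4, so 32 | 33 | 29 |

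The 43 reproduces. The 29 does not, and gives about 75% power by the t-test. Neither figure is tied to a torn versus tear-free comparison.

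If the groups are two equal parts of this cohort, 43 per group means 86 samples, against 82 patients to be enrolled and 74 to complete. With 37 per group (74/2), t-test power is 85% for 8 markers and 74% for 6. The timetable shows 54 patients completing the two-year evaluation by month 48. With 27 per group, power is 72% and 60%.

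**6. What could an added healthy group detect?** No document sizes this, so the following is an illustration. Assume 10 healthy fluids, a single marker, two-sided 0.05 and 80% power.

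Normal approximation, 74 patients: 2.802 × √(1/10 + 1/74) = 2.802 × 0.337 = 0.94 SD. The t-test gives 0.96 SD, and 0.98 with 54 patients or 0.95 with 82. With 10 against 74, power is 65% for a true difference of 0.8 SD and 31% for 0.5 SD.

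**The case against.** **An outside comparison is conceivable.** The laboratory has previously compared osteoarthritic fluid with healthy fluid by ELISA, and early-osteoarthritis synovium, obtained at arthroscopy for meniscal tears, with public healthy profiles. A reader might infer from the missing comparator that the question can never be answered. The documents do not support that. The limit lies in the samples and analyses as planned. An unplanned comparison with historical values would still be open to differences in assay run and donor selection.

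**Silence is not exclusion.** A reader might also infer that the plan rules out a tear-free group. Because the two groups are undefined, and 86 samples exceed planned enrolment, an outside group cannot be excluded. Nor is there evidence that one was meant. What can be said is that no comparator is named.

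**The sentence stands in the Background and the aim is exploratory.** The passage studies these patients because they are thought to have early osteoarthritis, so it could be read as describing complement in early disease. The cartilage-loss hypothesis needs no tear-free group and can be examined in this cohort. Both points lower the weight of the concern. But the text names the tear question as the focus of an aim, and exploratory status excuses low power rather than a missing contrast.

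**Adding healthy fluid would not isolate the tear.** This stands in full. The Background says nearly all such patients also have some chondromalacia or osteoarthritis, and the preliminary ELISA already reports C3a and MAC raised early in osteoarthritis. Torn versus healthy would mix the two conditions. The 10 healthy fluids belong to the proteomic survey. The text gives no healthy sample size for the ELISA, no donor ages and no statement that fluid remains.

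**Conclusion.** The concern holds in this form: from the samples and analyses planned, the association of tears with complement activation or synovial gene expression cannot be estimated, and the stated aim does not match the biomarker hypothesis. The mismatch follows from the text and needs no numerical assumption. The 0.96 SD figure rests on an assumed 10 usable controls and is only an illustration.

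The consequence is confined to what the exploratory work may conclude. The WOMAC outcome, Aim 2, the trial's sample size and its conduct are untouched, and the biopsy and fluid keep their use for the within-cohort hypothesis. The correction should be made because it costs almost nothing and removes a conclusion that the planned data cannot give.

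**What to change.** 1. Restate the Background aim as the association of complement, cytokine and cartilage markers at surgery with Outerbridge grade and with later cartilage loss. Drop the tear-association and gene-expression claims.
2. In the power section, define the two groups in those terms, correct the 29, and give power for the number expected to have the cartilage measurement. Say when serum is drawn, since the visit schedule lists no blood sample.
3. Optional: if stored healthy fluid exists, assay it in the same run as the trial samples with a stated C3a and C5b-9 contrast. Describe the result only as tear with early osteoarthritis versus healthy. Age adjustment may not be feasible with about 10 controls.

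Items 1 and 2 cost only wording and a short recalculation, with no added patients or procedures. The price is giving up the tear claim. Item 3 adds roughly ten samples to the assay run, if the assumed number is available, and remains sensitive only to large differences.

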Power calculations & bioinformatic analysis. We will test the hypothesis that increased complement activation, cartilage metabolism and/or inflammatory biomarkers are associated with accelerated cartilage loss. We will explore use of (i) predefined indexes of markers of cartilage metabolism (Table 3 above) and markers of inflammation (Table 4 above), and (ii) a combined multivariate test. For the predefined indexes of markers, we will standardize each marker to have standard deviation 1, so an average of 8 independent markers would have a variance 1/8, and an average of 6 a variance of 1/6. For the combined multivariate testing for the cartilage metabolism and the inflammatory markers, we will use 8 and 6 degrees of freedom, respectively, in conjunction with a multivariate Hotelling's T-test. Power calculation: So to achieve an effect (difference in mean index score) of .25 standardized units using a two-sample-test at (0.05 two-sided, power 0.8) would require 29 samples in each group for the 8-marker index, and 43 per group for the 6-marker index.

Statistical Analysis

Randomization:

We will explicitly test if randomization achieved balance between the experimental groups on potentially confounding variables such as age, gender, and body weight. However, confounding may still operate even if the differences between the groups are not statistically significant. Therefore, we will conduct two secondary analyses in which imbalances in important potential confounding variables (duration of symptoms, grade of chondromalacia found on arthroscopic evaluation of the joint, radiographic severity of arthritis (Kellgren-Lawrence), and diagnosis of depression) will be addressed. First, we will simply add these covariates to the primary regression model. However, estimating so many more parameters will inherently reduce the statistical power of the test of the intervention effect. Our second approach solves this problem by first calculating a propensity score (the probability of being in the meniscectomy group based on pre-treatment variables) for each patient, and then using the propensity scores as regression weights in the main regression analysis. This is a state of the art approach for estimating treatment effects in the presence of potential confounding.

Aim 1: *To test the clinical benefit of arthroscopic meniscectomy in the setting of a stable degenerative meniscus tear.*

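### The arthroscopic cartilage grade is recorded after the allocation envelope is opened, yet two secondary analyses adjust for it

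*Combined protocol and SAP*

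**What the plan says.** Research Design and Methods, Evaluation at the time of surgery, sets the order of events. "Randomization will be done by opening a sealed envelope in the operating room prior to the procedure". After that, "During the operation, the status of the knee joint will be documented". On the cartilage: "This will include classifying the degree of chondromalacia according to the Outerbridge classification in all three compartments of the knee". The tear geometry and pattern are documented at the same point. Tears without a displaceable unstable flap "will be either retained or debrided, depending on the result of randomization", so the operating team has to know the arm while it works.

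Two other sentences there bear on the point. "Video and photographs will be taken to assist with this documentation and will be stored in a secure manner". And on masking: "All postoperative contact from this point forward will be made by study personnel who were not involved in the surgery", by people who do not know the allocation. No masked or independent reading of the cartilage is specified, and nothing requires the grade to be fixed before the envelope is opened.

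Statistical Analysis, Randomization, then lists four potential confounders: duration of symptoms, "grade of chondromalacia found on arthroscopic evaluation of the joint", Kellgren-Lawrence grade and a diagnosis of depression. Two secondary analyses are to address imbalance in them. The first adds the covariates to the primary model. The second uses a propensity score, defined as "the probability of being in the meniscectomy group based on pre-treatment variables", as regression weights.

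**The concern.** A covariate in a randomized comparison should be fixed before allocation is known, or be of a kind that knowledge of the arm cannot change. Symptom duration, Kellgren-Lawrence grade and depression diagnosis can all be fixed before the envelope is opened. The Outerbridge grade, as sequenced, is not. It is a judgement made by eye after allocation, in a room where the arm is known.

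If knowing the arm shifts the grading even slightly, the shift looks like a chance imbalance between arms, and the adjustment removes an imbalance that does not exist. The unadjusted comparison stays unbiased while the adjusted one moves. The analyses exposed are those meant to reassure a reader about confounding.

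**Working it through.** **1. Order of events against use of the variable**

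- Envelope: before the procedure (Evaluation at the time of surgery).
- Outerbridge grade: during the operation, so after the envelope (same section).
- First secondary analysis: the grade is explicitly among the added covariates (Statistical Analysis, Randomization).
- Second secondary analysis: the inputs to the propensity score are not listed. The paragraph offers it as the second way to handle the same four confounders, so inclusion of the grade is a close inference.
- Grader: not named. That the grader knows the arm is also a close inference.

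**2. The plan's own figure and the scale for bias**

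Hypothesis 1a uses 37 per arm, SD 392 and a difference of 260.

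- Standard error of the difference = 392 × √(2/37) ≈ 91 points.
- Normal-approximation power = Φ(260/91.1 − 1.96) = Φ(0.89) ≈ 81.4%. The noncentral t gives 80.4%. The stated 81% is reproduced, and this point does not alter it because that test has no covariate.

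**3. Bias under modest assumptions**

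The documents give none of these inputs. Assume no true treatment effect, half the knees in a higher cartilage grade, β WOMAC points between the two grades (100 to 200), and a fraction q of lower-grade knees in one arm graded up (0.10 to 0.20).

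- Difference between arms in the proportion recorded as higher grade = 0.5q.
- Pooled within-arm slope of the outcome on the recorded grade = β(2 − q)/(2 − q²).
- Bias of the adjusted difference = −β × 0.5q × (2 − q)/(2 − q²).

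| β | q | Bias (points) | Bias / 91 |
|---|---|---|---|
| 100 | 0.10 | −4.8 | 0.05 |
| 200 | 0.10 | −9.5 | 0.10 |
| 100 | 0.20 | −9.2 | 0.10 |
| 200 | 0.20 | −18.4 | 0.20 |

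The sign reverses if the other arm is graded up. The unadjusted difference has no bias in any row.

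If the propensity weights are read as inverse-probability weights, the bias is −β × [q/(1 + q)] × (0.5 + 0.25q). That gives −4.8 points at β = 100, q = 0.10 and −18.3 at β = 200, q = 0.20, so on that reading the second analysis gives no protection.

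Effect on a nominal 5% two-sided test, for a shift of s standard errors: Φ(−1.96 + s) + Φ(−1.96 − s). At s = 0.05 this is 5.0%; at s = 0.20 it is 3.9% + 1.5% ≈ 5.5%.

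**4. Is 100 to 200 points reasonable?**

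The pilot (Preliminary Studies) gives mean WOMAC improvement of 656 in radiographic grades 0–1 and 561 overall. If a share f of patients was in grades 0–1, the gap to grades 2–3 is (656 − 561)/(1 − f) = 95/(1 − f). The share is not given; for f of 30% to 60% the gap is about 136 to 238. This is a radiographic grade and a change score, so only a loose proxy.

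**5. Stress case**

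A simulation used 37 per arm, total SD about 392, a five-level grade with shares 10/25/30/25/10%, and 50, 100 or 200 points per grade.

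- No differential grading: adjusted bias within 3 points, type I error 4.4–5.1%.
- 25% of one arm graded up a step: bias about −11, −21 and −43; type I error 5.0%, 6.0% and 8.8%.
- 50% graded up: bias about −21, −47 and −86; type I error 5.5%, 7.7% and 19.3%.
- Unadjusted t-test: about 5% throughout.

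No figure in the documents supports up-grading on that scale. These rows show only how the bias grows.

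**The case against.** The strongest reply is that the effect is negligible where it counts. The primary analysis is an unadjusted t-test, its stated sensitivity analysis is a t-test on change scores, and Hypothesis 1b rests on confidence limits for a difference in means. None of these names a covariate. That stands. A reader might infer that the trial's main result, or its 194-point non-inferiority margin, is at risk; the documents do not support that.

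It can also be said that the damage itself predates treatment, that differential grading is a possibility rather than something shown, and that its direction is unknown. All of this stands. The only route to bias is knowledge of the arm at the moment of grading.

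A reader might further infer that the trial could never tell a true imbalance from a grading artefact. That is too strong. Video and photographs are taken and stored, and every patient has preoperative standing radiographs and a knee MRI whose protocol covers cartilage thickness, so an arm difference in the arthroscopic grade could be checked. Any divergence between adjusted and unadjusted results would also be visible. What remains is narrower: no masked reading is planned, and nothing requires footage to be captured before resection for that purpose.

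Finally, it would overstate the text to say as fact that the surgeon does the grading or that the grade enters the propensity score. The first analysis needs no inference about inclusion: the grade is named there.

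**Conclusion.** The point holds as a small procedural gap. A subjective covariate is recorded after allocation, with no masked reading and no rule fixing it beforehand, and is then used as though it were a pre-allocation measure. One secondary analysis is exposed explicitly and the other by close inference.

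Under the modest assumptions above, the bias is about 5 to 18 WOMAC points, or 0.05 to 0.2 of a 91-point standard error, and it moves a 5% error rate to at most about 5.5%. It becomes material only if a large share of one arm is graded differently, which nothing in the documents suggests. The reason to act is that the exposure is nearly free to remove and sits in the analyses offered as protection against confounding.

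**What to change.** Under Evaluation at the time of surgery, require the Outerbridge grades and tear geometry from the diagnostic look to be recorded and time-stamped before the envelope is opened. The grade used under Statistical Analysis is then a genuine pre-allocation variable. No extra patients or assessments are needed; the envelope is opened a few minutes later, during the arthroscopy.

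If the envelope must stay first, there are two alternatives:

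- Have the grade read from the video already planned, using only pre-resection footage and with the arm masked. This costs reader time and a requirement that such footage be captured for every patient.
- Drop the arthroscopic grade from both secondary models and keep the preoperative Kellgren-Lawrence grade, already listed, as the severity covariate. This loses one severity covariate.

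In either case, list the inputs to the propensity score by name and state when each is measured.
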